### Intervals from First OLE-IEDAT Infusion

Adverse Event analysis outlined in Section 10.7.1 is displayed overall and in 12 month intervals from first OLE-IEDAT Infusion.

These are derived by calculating day since First OLE-IEDAT Infusion:

$$\text{Day since First OLE-IEDAT Infusion} = (\text{Date of event} - \text{Date of First OLE-IEDAT Infusion})$$

This is then mapped to 12 months intervals as follows:

| Interval        | Window              |
|-----------------|---------------------|
| 0 to 12 months  | Day in [0, 364]     |
| 12 to 24 months | Day in [365, 729]   |
| 24 to 36 months | Day in [730, 1094]  |
| 36 to 48 months | Day in [1095, 1459] |
| 48 to 62 months | Day in [1460, 1824] |
| ...             | ...                 |

### Continuous Exposure

Continuous exposure is derived in 12-month intervals with a patient being determined to have continuous exposure if they have a maximum of one month treatment interruption within any 12 month interval. The 12-month interval of continuous exposure may start at any dosing visit. Data on continuous exposure may be used for future exploratory analysis.

## Study Day

For event type data the Study Day of an event is calculated relative to the Date of First OLE-IEDAT Infusion as defined above. The Study Day of events occurring before the Date of First OLE-IEDAT Infusion is calculated as:

$$\text{Study Day} = (\text{Date of event} - \text{Date of First OLE-IEDAT Infusion}).$$

For events/assessments occurring on or after the date of First OLE-IEDAT Infusion, Study Day is calculated as:

$$\text{Study Day} = (\text{Date of event} - \text{Date of First OLE-IEDAT Infusion}).$$

## OLE-IEDAT Baseline

*Final evaluations for the IEDAT-02-2015 trial will serve as baseline evaluations for patients continuing in the IEDAT-03-2018 study. The following “baseline” assessments for IEDAT-03-2018 will be done as part of the final Visit 15 evaluation in Study IEDAT-02-2015: physical/neurological examination; 12-lead standard ECG; laboratory evaluations [including hematology, clinical chemistry, urinalysis, serum pregnancy test (women of childbearing potential); special laboratory tests: HbA1c, CD4+ lymphocytes count and CRP]; assessment of physical development, sexual maturation, and the effect of treatment with dexamethasone on these aspects (Tanner scale); ICARS; CGI-S; CGI-S; EQ-5D-5L; C-SSRS; BMD; review of AEs and concomitant medications.*

If values are missing at the baseline visit, and the data are also recorded at screening, then the screening value are used in the summaries and calculations of change from baseline. Otherwise, the baseline value is missing for safety and efficacy endpoints.

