- \* Applicable only for patients which will be enrolled without completing the ATTeST trial (i.e. who were discontinued from the Study IEDAT-02-2015 during the COVID-19 pandemic), and which may not have final evaluations for IEDAT-02-2015 study (Visit 15/Month 12). Patients signing the informed consent form or assent, as applicable, at this visit do not need to re-consent at baseline visit.
- &) The following “baseline” assessments for IEDAT-03-2018 will be done as part of the final Month 12 evaluation in Study IEDAT-02-2015: physical/neurological examination; 12-lead standard ECG; laboratory evaluations [including hematology, clinical chemistry, urinalysis, serum pregnancy test (women of childbearing potential); special laboratory tests: HbA1c, CD4+ lymphocytes count and CRP]; Tanner scale; ICARS; CGI-S; CGI-C; VABS: EQ-5D-5L; C-SSRS; BMD; Review of AEs and concomitant medications.
  - a) Routine laboratory assessments to include complete hematology, biochemistry, and urinalysis.
  - b) Special laboratory tests include HbA1c, CD4+ lymphocytes count and CRP.
  - c) Blood sample to be collected before 8:00 AM for measurement of plasma cortisol at the following times: (1) when patients are symptomatic, and (2) when patients are at most risk for adrenal insufficiency and adrenal crisis, such as following discontinuation or interruptions of dexamethasone dosing (i.e., loading failures and following discontinuation of the study drug).
  - d) For women of childbearing potential only. The test results must be negative at baseline (urine) for the patient to be eligible for the study. Urine pregnancy test will be performed before every infusion, while serum pregnancy test will be performed at Month 6, 12 and safety follow up visit.
  - e) A Safety Follow-up assessment will be performed approximately 60 days ( $\pm 7$  days) after the final infusion; at this visit, plasma cortisol, pregnancy status (for women of childbearing potential), vital signs will be assessed, as well as the occurrence of any AEs or Serious AEs since the final evaluation will be reported.
  - f) Upon completion of the EDS process, the remaining sample in the satellite sample bag or, if this is not available, a sample collected from another EDS-EP sampling point will be used for determination of DSP content and CBC.
  - g) Blood sample for serum creatinine measurement to be taken before infusion.

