### 16.2 Statistical Methods

#### 16.2.1 *Sample Size*

There is no formal sample size calculation, as the sample size is dependent on the number of patients who complete the double-blind extension study (Protocol IEDAT-02-2015), express the desire to continue treatment with the investigational drug, and meet the selection criteria defined in [Section 9.2](#) of the Study IEDAT-03 protocol. It is expected that a maximum of 150 patients will enter this open-label extension.

The following analysis sets will be used:

- 1) *Efficacy Population (EP)*: All patients who enter study IEDAT-03, have a baseline efficacy assessment in study IEDAT-03, and who received at least one dose of study medication and had at least one post-baseline efficacy assessment of the primary efficacy variable in this extension study.
- 2) *Safety Population (SP)*: All subjects who receive a dose of study medication, and have at least one post-dose safety assessment will be included in the safety analyses.

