### 3.3 Study Schedule

#### Screening phase

The screening phase is *applicable only for patients which will be enrolled without completing the ATTeST trial. The screening phase will last a maximum of 30 days. Any previous treatments with corticosteroid compounds will be withdrawn (washout from previous treatment), while for other patients the screening phase may coincide with the screening visit (1 day long, provided that all the required laboratory reports are available and reviewed before the eligibility confirmation at the baseline). As soon as all screening assessments/procedures have been performed and eligibility is confirmed, the patients can undergo the baseline visit.*

*If any abnormal laboratory test results, vital sign measurements, or ECG findings of clinical significance are noted at the screening visit, these must be repeated during the 30-day screening period and the results made available prior to making the final decision on a patient's eligibility for the study at Baseline.*

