| EDS end product sample (f)            |                                      | X (post)                   | X (post)  | X (post)  | X (post)  | X (post)  | X (post)  | X (post)      | X (post)  | X (post) | X (post) | X (post) | X (post) | X (post)      |                              |
| Prior/Concomitant Treatments          | Throughout the duration of the study |                            |           |           |           |           |           |               |           |          |          |          |          |               |                              |
| Adverse Events                        | Throughout the duration of the study |                            |           |           |           |           |           |               |           |          |          |          |          |               |                              |

- \* Applicable only for patients which will be enrolled without completing the ATTeST trial (i.e., who were discontinued from the Study IEDAT-02-2015 during the COVID-19 pandemic), and which may not have final evaluations for IEDAT-02-2015 study (Visit 15/Month 12). Patients signing the informed consent form or assent, as applicable, at this visit do not need to re-consent at baseline visit.
  - &) The following “baseline” assessments for IEDAT-03-2018 will be done as part of the final Month 12 evaluation in Study IEDAT-02-2015: physical/neurological examination; 12-lead standard ECG; laboratory evaluations [including hematology, clinical chemistry, urinalysis, serum pregnancy test (women of childbearing potential); special laboratory tests: HbA1c, CD4+ lymphocytes count and CRP]; Tanner scale; ICARS; CGI-S; CGI-C; EQ-5D-5L; C-SSRS; BMD; Review of AEs and concomitant medications.
- a) Routine laboratory assessments to include complete hematology, biochemistry, and urinalysis.
  - b) Special laboratory tests include HbA1c, CD4+ lymphocytes count and CRP.
  - c) Blood sample to be collected before 8:00 AM for measurement of plasma cortisol at the following times: (1) when patients are symptomatic, and (2) when patients are at most risk for adrenal insufficiency and adrenal crisis, such as following discontinuation or interruptions of dexamethasone dosing (i.e., loading failures and following discontinuation of the study drug).

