### 6.3 Subgroup Definitions

Patients are grouped by their treatment group in the ATTeST study: EDS-EP Low Dose, EDS-EP High Dose, Non-switch Placebo, Visit 9 Low Dose, Visit 9 High Dose, Visit 12 EDS-EP Low Dose, and Visit 12 High Dose. All outputs contain columns to display these groups.

The following endpoints are also summarised by subgroups for Age (<10; ≥10 years) and Region (India; Europe, Australia, and Tunisia; United States):

- ICARS
- mICARS
- RmICARS
- CGI-C
- CGI-S
- EQ-5D-5L

Patients with a treatment gap of greater than 76 days between the ATTeST study and the OLE-IEDAT study are presented as a separate subgroup for outputs as outlined in Section 10.

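### When a patient has both an ATTeST final value and a later OLE screening value, SAP 7.1 appears to keep the older one as OLE baseline, so change over the gap counts as open-label change

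*SAP*

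**What the plan says.** SAP 7.1, under OLE-IEDAT Baseline, states the general rule: "Final evaluations for the IEDAT-02-2015 trial will serve as baseline evaluations for patients continuing in the IEDAT-03-2018 study". Its list of such assessments includes ICARS, CGI-S, EQ-5D-5L, laboratory tests and BMD. A second paragraph adds the fallback: "If values are missing at the baseline visit, and the data are also recorded at screening, then the screening value are used". It closes: "Otherwise, the baseline value is missing for safety and efficacy endpoints".

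SAP 3.3 says the OLE screening phase is "applicable only for patients which will be enrolled without completing the ATTeST trial". The footnote to the schedule (Protocol 11.3, Table 2; repeated in SAP Table 1) describes these as patients discontinued during the pandemic "which may not have final evaluations for IEDAT-02-2015 study (Visit 15/Month 12"). Their screening, at Day -30 to -1, repeats ICARS, CGI-S, EQ-5D-5L, BMD, and routine and special laboratory tests.

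SAP 7.4.7, 7.4.8 and 10.7.10 plan changes from OLE baseline for mICARS, RmICARS, full ICARS, EQ-5D-5L index, laboratory tests and BMD z-scores. None is adjusted for the time between baseline and first OLE infusion. SAP 6.3 defines a separate subgroup: "Patients with a treatment gap of greater than 76 days between the ATTeST study and the OLE-IEDAT study".

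**The concern.** A baseline should describe the patient at the start of the treatment being evaluated. Here a value taken before a treatment gap can take precedence over one taken within 30 days before the first OLE infusion. Whatever happened in between is then reported as change on open-label EDS-EP.

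The protocol gives reason to expect such change. It describes AT as relentlessly progressive (7.3 and 12.1.2), and it reports that symptoms came back after betamethasone was stopped in small, short, uncontrolled studies (7.3). For safety, which is the primary objective, the distortion need not point one way. In the pilot, two patients stopped after CD4+ falls of more than 20% judged related to treatment (Protocol 7.1.3.1). If CD4+ recovered during a gap and fell again in the extension, a pre-gap baseline could show little change and hide the second fall.

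The wording also leaves room for two programmers to derive different baselines. SAP Table 2 and Protocol 11.4.2 attach the baseline label to Visit 1/Day 0, whereas the first paragraph of the SAP rule takes baseline from ATTeST Visit 15.

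**Working it through.** The plan has no figure of its own to reproduce. Protocol 16.2.1 says "There is no formal sample size calculation", and the SAP plans descriptive summaries only. The check is to apply the rule to each type of patient and then to scale the result.

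**Step 1: which values can exist.** The schedule has no ICARS, CGI-S, EQ-5D-5L, BMD, routine laboratory or special laboratory assessment at Visit 1. For these, the only possible pre-infusion sources are the ATTeST final evaluation and OLE screening. Completers have no OLE screening. Patients who did not complete ATTeST have screening and may or may not have an ATTeST final value.

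**Step 2: apply the rule.** As an illustration, take an mICARS of 30 at the ATTeST final evaluation, 33 after the gap, and 33 at follow-up. The patient worsens by 3 points in the gap and not at all on open-label treatment. Change = follow-up minus OLE baseline.

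- Reading A: a value is missing at the baseline visit if the ATTeST final value is missing.
- Reading B: a value is missing at the baseline visit if nothing was recorded at Visit 1/Day 0.

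| Patient | ATTeST final | OLE screening | Reading A | Reading B | Last value before first OLE infusion |
|---|---|---|---|---|---|
| Completer | 30 | none | baseline 30, change +3 | baseline missing | baseline 30, change +3 |
| Non-completer, no ATTeST final value | none | 33 | baseline 33, change 0 | baseline 33, change 0 | baseline 33, change 0 |
| Non-completer with both values | 30 | 33 | baseline 30, change +3 | baseline 33, change 0 | baseline 33, change 0 |

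Reading B leaves every completer without an efficacy baseline, which contradicts the opening sentence of the same rule. Reading A is coherent, and under it only the third row is distorted in a way that the rule could have avoided.

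**Step 3: scale.** For an affected patient the distortion is the screening value minus the ATTeST final value, approximated as rate per year × days / 365. The documents give no mICARS progression rate, gap distribution or count of patients with both values. I assume 1 to 4 points a year and 76 to 365 days. The 76 is the SAP 6.3 treatment-gap threshold, used only for scale. The interval between the two assessments is not identical to the treatment gap, and screening may precede the first infusion by up to 30 days.

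- 1 × 76/365 = 0.21 points
- 4 × 76/365 = 0.83 points
- 1 × 365/365 = 1.0 point
- 4 × 365/365 = 4.0 points

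The shift in a group mean is this figure times the share of patients affected. With an assumed share of 5% to 30%, it runs from 0.05 × 0.21 = 0.01 to 0.30 × 4.0 = 1.2 points.

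**The case against.** The strongest objection is that the affected group may be empty. Protocol 9.2.1 sets out two entry routes: completing the Visit 15 efficacy assessments, or discontinuing during the pandemic. The footnote says screened patients may lack final evaluations, so an overlap is possible but not shown. For a screened patient without an ATTeST final value, the fallback already gives a post-gap baseline. This stands, and it limits the reach of the point.

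A second objection is that the SAP can be read by entry route: the first paragraph for continuing patients, the second for screened ones. That would give the right baseline in every row of the table. But the sentence depends on a value being missing, not on route of entry, so the route reading would have to be written in.

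Third, SAP 6.3 separates patients with long gaps. This is a partial safeguard. However, SAP Sections 10 and 12 list no output for that subgroup, and SAP 9 says it is not required for the Briefing Book and NDA analyses.

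Fourth, the analyses are descriptive with no hypothesis tests, and counting gap decline against EDS-EP cannot produce a false efficacy claim. This stands for efficacy. It does not settle the safety parameters.

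A reader might infer that every change from OLE baseline is distorted. The documents do not support that:

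- Weight is measured at Visit 1 itself.
- CGI-C is recorded by the rater and is not derived from this rule.
- CGI-S is summarised only as categories in SAP 10.6.1, although Protocol 16.2.6 does foresee a mean change.
- Changes from ATTeST baseline do not use this rule.

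A reader might also set the distortion against the pilot improvement of about 4 points. That improvement was on the full 100-point ICARS, whereas mICARS runs from 0 to 54, so the two are not on one scale.

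**Conclusion.** The point holds as a gap in the baseline definition with limited reach. On the coherent reading, a patient with both values keeps the older one, and change over the gap is reported as open-label change in mICARS, RmICARS, ICARS, EQ-5D-5L index, laboratory and BMD change scores. The distortion is about 0.2 to 4 mICARS points per affected patient under the assumed rates and gaps. Its effect on a group mean could be negligible, because the share of patients with both values is unknown. For efficacy, gap decline makes EDS-EP look worse; for safety the direction is open.

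The >76-day subgroup might be taken as evidence that many patients are affected. It is not, because it covers any patient with a long gap, including completers who started late. Those completers have no later efficacy value, so no choice between recorded values can change their efficacy baseline. Nor is the interval always a period off drug: for patients on placebo to the end of ATTeST it is simply continued untreated time.

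**What to change.** In SAP 7.1, replace the fallback sentence with a definition per parameter: OLE baseline is the last non-missing value before the first OLE infusion, whether from the ATTeST final evaluation, OLE screening or pre-dose Visit 1. Flag the source of each baseline value, and report the days from baseline to first OLE infusion.

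This removes the avoidable distortion wherever both values exist and settles what is meant by the baseline visit. For completers with a delayed start it leaves the efficacy baseline as it is but makes its age visible. The cost is one SAP sentence, a source flag and an interval variable; no new data are needed.

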## ATTeST Baseline

For some analyses a comparison with the baseline value of the ATTeST study is to be performed. PPD receives datasets where it is clearly marked which values are to be regarded as ATTeST baseline for these analyses.

## Repeated evaluations

The interruption of an EDS process can result in a repeat EDS process with potentially the repeat of assessments that are scheduled to take place prior to the EDS process at a given visit. If this occurs (a repeat EDS process is conducted and the assessments scheduled to take place prior to an EDS assessment are repeated), the set of assessments recorded under the nominal visit label are used.

## 7.2 Event Dates

Medical events are defined as medical history, prior and concomitant medication, non-drug therapy and procedures, and adverse events.

### 7.2.1 Event Days

All types of events have a Start/Onset Day calculated and, if not ‘Ongoing’, have a Stop/Resolution Day calculated equivalent to Study Day as defined in 7.1.

### 7.2.2 Missing Dates and/or Times

Missing and/or incomplete dates/times for events are imputed for calculating Start Day and Stop Day only. Dates are listed as missing/incomplete [with “-“ replacing missing information] but the Start/Stop Day/Time are listed between square brackets to denote it is calculated based on missing data (i.e. [-28], [1], [Ongoing]).

Missing and/or incomplete dates/times are imputed in a manner that assumes the worst-case scenario (i.e., Start as close as possible to the First Study Treatment Administration and stopped such that it is assumed to have lasted for the longest possible duration, taking into account that the Start date/time should not be after the Stop date/time).

Technically, this is done as follows for Stop Day/Time:

- For a completely missing stop year (regardless of minute, hour, day or month response) the event is assumed to be ongoing.
- For a missing stop hour (and the event is not 'Ongoing'):
  - it is assumed to have ended on hour 23 (11pm) of that day
- For a missing stop minute (and the event is not 'Ongoing'):
  - it is assumed to have ended 59 minutes past the hour
- For a missing stop day (and the event is not 'Ongoing'):
  - it is assumed to have ended on the last day of the month, if the month is given
  - it is assumed to have ended on the 31st of December of that year, if the month is also missing

Technically, this is done as follows for Start Day/Time:

- For a completely missing Start date (day, month and year regardless of the minute and hour recorded)
  - the Start Day of the event is "[Pre-Treat]" if the stop date or partial stop date concludes the event stopped before First Study Treatment Administration (i.e., assumed to be prior or pre-treatment as is applicable).
  - in all other instance (i.e., inconclusive stop date or Ongoing event) the Start Day of the event is assumed to be the same date and time as First Study Treatment Administration (i.e., assumed to be concomitant or treatment emergent as applicable.)
- For a missing start hour:
  - it is assumed to have started on hour 00 (midnight) of that day.
  - or at the time (hour and minute) of First Study Treatment Administration if the start date (day, month and year) is the same as the First Study Treatment Administration date.
- For a missing start minute:
  - it is assumed to have started on minute 00 of that hour.
  - or at the time (hour and minute) of First Study Treatment Administration if the start date (day, month and year) is the same as the First Study Treatment Administration date.
- For a missing Start day but given month:
  - it is assumed to have started on the first day of the month.
  - or at the date of First Study Treatment Administration if the start month and the year is the same as the First Study Treatment Administration month and year.
- For a missing start month:
  - it is assumed to have started on the first of January of that year.
  - or at the date of First Study Treatment Administration if the start year is the same as the First Study Treatment Administration year.

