#### **Adverse Events During COVID-19 treatment interruptions**

For patients with treatment interruptions that result in gaps in dosing of greater than 60 days, adverse events are only considered treatment emergent if they occur within 60 days following the last dose. Adverse events that occurred greater than 60 days following the last dose will not be considered treatment emergent. For this population of patients whose long treatment interruption was due to COVID-19, three types of summarizations will be prepared:

- On dose (treatment emergent) adverse events
- Off dose (not treatment emergent) adverse events. Off dose events are those that occur during a period >60 days following a dose and prior to the immediately following dose.
- Restart (TEAE after restart of treatment) adverse events. Restart events are those that occur on/after the first dose after an off-dose period and prior to the start of any following off dose period.

Times to be considered as treatment interruptions due to Covid-19 are provided by EryDel in form of an excel spreadsheet.

|   |         |  |
|---|---------|--|
| CD+4 Lymphocyte count   | x10E9/L | Month 6 and Month 12   |
| Early morning Plasma Cortisol testing for Adrenal Insufficiency | µg/dL   | As needed: when patients are symptomatic, and when patients are at most risk for adrenal insufficiency and adrenal crisis, such as following discontinuation or interruptions of dexamethasone dosing |
| High dose ACTH stimulation test                                 | µg/dL   | As needed: In the event that patients show signs or symptoms of adrenal insufficiency during the study  |

All laboratory assessments are performed at local laboratories. Quantitative laboratory results are converted to their respective Reporting units for use in summary tables. Assessment of results as being within the normal range are made by the local laboratory. *Any laboratory abnormalities meeting the definition of an adverse event should be recorded on the Adverse Events CRF.*

Clinically notable values of standard laboratory are derived based on SI units as outline in Appendix 13.1.

If repeat tests are performed at any visit the result documented under the nominal visit label is used in all summaries and analyses for that Visit.

Baseline is as described in Section 7.1.

The change from baseline is calculated for quantitative laboratory tests at each scheduled post-baseline visit as:

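### The worst-case partial-date rule in SAP 7.2.2 has no exception for a restart month, so after a long COVID-19 gap an AE dated only to that month is classed as off dose and not treatment emergent

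*SAP*

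**What the plan says.** SAP 7.2.2 (Missing Dates and/or Times) states its principle as follows: "Missing and/or incomplete dates/times are imputed in a manner that assumes the worst-case scenario". For start dates it explains this as "Start as close as possible to the First Study Treatment Administration".

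The rules for a partial start date are:

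- Day missing, month known: "it is assumed to have started on the first day of the month". The exception is the date of the first administration, used "if the start month and the year is the same as the First Study Treatment Administration month and year".
- Month missing: "it is assumed to have started on the first of January of that year". The exception is again the first administration, used "if the start year is the same as the First Study Treatment Administration year".

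No later infusion is named.

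SAP 7.4.8 (Adverse Events During COVID-19 treatment interruptions) covers patients with dosing gaps of more than 60 days. AEs up to 60 days after the last dose are on dose and emergent. AEs later than that and before the next dose are off dose and not emergent. The third class is defined by the resumption of treatment: "Restart events are those that occur on/after the first dose after an off-dose period". This subsection has no partial-date rule of its own. Table 14.3.1-1.10 reports the off-dose AEs and Table 14.3.1-1.11 the restart AEs.

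**The concern.** The 7.2.2 rule is worst case only where emergence turns on a single date, the first dose. For patients with a COVID-19 gap, 7.4.8 adds a second such date, the restart dose. When an AE is known only to the month of restart, the default of the 1st normally places it before that dose. After a long gap that means the non-emergent class, which is the most favourable reading and the opposite of what 7.2.2 promises.

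At stake is the restart table, which exists to show what happens on re-exposure. It can lose events to the off-dose table, always in the same direction.

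**Working it through.** The documents give no misclassification rate to reproduce, so the check applies the stated rules day by day.

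**Inputs from the SAP.** Missing day becomes day 1, with the first-administration month as the only exception (7.2.2). Off dose means more than 60 days after a dose and before the next one; restart means on or after that next dose (7.4.8).

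**Assumptions not in the documents.** A 30-day restart month; restart day r uniform on 1 to 30; onset day uniform on 1 to 30; gap G (days from last dose to restart) varied.

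**One case.** Take a last dose on 10 March 2020, a restart on 15 September 2020 (G = 189) and an AE recorded as September 2020. The imputed start is 1 September, which is 189 − 14 = 175 days after the last dose and before the restart. The AE is off dose and not emergent. Yet 16 of the 30 possible onset days (15 to 30 September), or 53%, are on or after the restart.

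**General condition.** Day 1 lies G − (r − 1) days after the last dose. The AE is put off dose when r > 1 and G − (r − 1) > 60. For the latest restart day, r = 30, this needs G > 89. So from G = 90 every restart after the 1st qualifies. In a 31-day month the same step gives G = 91.

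**Truth under uniform dates.** The share starting on or after the restart is the mean of (31 − r)/30, which is 15.5/30 = 51.7%. The share starting before it is 14.5/30 = 48.3%.

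**Result of the rule for G ≥ 90.** For 29 of 30 restart days (96.7%) every such AE goes off dose. The share of all these AEs that are true restart events placed off dose is the sum of (31 − r) over r = 2 to 30, divided by 30 × 30: 435/900 = 48.3%.

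**Shorter gaps.**

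| Gap G (days) | Restart days that send the AE off dose | Restart days that send it on dose | True restart AEs put off dose (share of all) |
|---|---|---|---|
| 61 | 0% | 96.7% | 0% |
| 65 | 13.3% | 83.3% | 12.2% |
| 70 | 30.0% | 66.7% | 25.0% |
| 75 | 46.7% | 50.0% | 35.0% |
| 80 | 63.3% | 33.3% | 42.2% |
| 90 or more | 96.7% | 0% | 48.3% |

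The remaining 3.3% in each row is a restart on the 1st, which the rule classes correctly as restart.

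**The case against.** Several points can fairly be made for the plan.

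- **Scope of the imputation.** 7.2.2 says dates are imputed only to calculate Start Day and Stop Day. But the same section says that an imputed start can make an event treatment emergent, and 7.4.8 offers no other rule. Using the imputed day for the split is the natural reading. If it is not intended, the split has no rule for partial dates at all.
- **General TEAE definition.** Elsewhere in 7.4.8, all AEs during the extension are declared TEAEs. If that governs, the main TEAE tables do not change. This stands. The two passages conflict, but the division between Tables 14.3.1-1.10 and 14.3.1-1.11 is affected either way.
- **Nothing disappears.** The AEs still appear in the neighbouring table and in the listings, where imputed days are bracketed. This stands.
- **Few cases.** Protocol 14.1.2 asks for onset date and time, visits are monthly, and 18.5.2 does not allow unexplained blanks. Partial dates may well be rare.
- **Gap between the two studies.** The first study treatment administration is not among the dates defined in 7.1. If it means the first infusion in this study, a gap between ATTeST and the extension is already handled.

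A reader might also infer that the by-period AE table is badly distorted, because AE analysis "is displayed overall and in 12 month intervals from first OLE-IEDAT Infusion" and year-only dates move to 1 January. A shift to an earlier period in about half of cases holds only as an average for year-only AEs in full calendar years after the first-infusion year. Over all year-only AEs, with uniform onset and first-infusion dates, the average is 0%, 25%, 33%, 37% and 40% for 1 to 5 years of exposure, and the planned treatment period is 12 months. For month-only dates it is about 4%. That does not support a change to the period table.

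**Conclusion.** The point holds in a limited form. The rule is anchored on the first dose alone, while for patients with a COVID-19 gap the classification also depends on the restart dose. A month-only AE in the restart month becomes off dose and non-emergent if the restart is after the 1st and the 1st is more than 60 days after the last dose. Under uniform dates and a gap of 90 days or more, about 48% of such AEs are true restart events reported as off dose.

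Two wider inferences are not supported. First, not every month-only AE in a restart month goes off dose: a restart on the 1st is classed correctly, and for gaps of 61 to 89 days many such AEs become on dose, which is emergent though not restart. Second, distortion of the overall long-term safety result is not shown. The certain effect is on two COVID-19 tables, and any effect on the main TEAE tables depends on which of the two emergence rules governs. The percentages apply to an unknown number of partial dates, so the effect on the tables cannot be sized and may be small.

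**What to change.** Add one exception to the missing-start-day rule in SAP 7.2.2: if the known month and year contain the first dose after an off-dose period, and the 1st of that month would be off dose, the start is imputed to that restart dose date unless the stop date is earlier.

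The cost is one sentence in the SAP and a few lines of ADaM code, with no new data. The price in accuracy should be stated openly. Under uniform dates about 48% of these AEs truly precede the restart and would now count as restart events, apart from those that a stop date shows to have ended earlier. For gaps of 90 days or more, no true restart AE in that month would be left off dose. This exchanges one error for another of similar size, but in the conservative direction that 7.2.2 claims.

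The exception should not extend to year-only dates. In the worked case, with regular dosing up to March, an AE dated only 2020 is set to 1 January 2020 and is already on dose and emergent. Moving it to 15 September would create an artificial restart event.
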